6.11 Interim Analysis

The main purpose of the interim analysis is to re-estimate the sample size. The sample size estimate described in the sample size [Section 6.10](#) is based on effect size assumptions from the Phase 2 data in which the primary endpoint was the change from baseline to endpoint in R-MOAS ratings. However, the primary endpoint for this study is percent change in the frequency of IA incidence per 7 days in the Treatment (Titration and Maintenance) period (PCH_T) relative to the Baseline period in the ITT population calculated over the number of days with non-missing IA diary data. Hence, there is uncertainty as to what magnitude of alternative hypothesis treatment difference and between-subject variability is appropriate to pre-specify. To this end, a single interim analysis is planned after approximately 50% of subjects complete the study. The adaptive design plan for the interim analysis plan is presented in the [Appendix 10.1](#).

6.12 Assessment of MCIC

Based on unblinded data available at study close, the ability of a percent change (PCH) endpoint to detect change will be evaluated using three anchor-based minimal clinically important change (MCIC)

estimates obtained from two global impression of change (CGI-I) variables and one global impression of severity (CGI-S) variable. Consistent with the recommendations of Hays (Hays et al., 2005), the assessment of detection of clinically meaningful change will emphasize unstandardized anchor-based estimates "so that users of the measure will be able to interpret differences in the raw metric."

[figure not shown]
The anchor-based MCIC values will be obtained by estimating the average PCH for minimal improvement groups defined by ratings from two raters for two concepts. Investigators and caregivers will each rate global impression of change. These will be known as Investigator-rated CGI-I and Caregiver-rated CGI-I, respectively. However, only investigators will rate global impression of severity (CGI-S). These CGI-I/CGI-S measures will be obtained at multiple site visits (Visit 3, Visit 4, Visit 5, and Visit 6) throughout the study period to reduce recall error and quantify incremental change over time. Investigator-rated CGI-I and Caregiver-rated CGI-I will be assessed on a 7-point scale with 1=Very much improved, 2=Much improved, 3=Minimally improved, 4=No change, 5=Minimally worse, 6=Much worse, and 7=Very much worse. CGIS will be evaluated on a 7-point scale with 1=Normal, 2=Borderline ill, 3=Mildly ill, 4=Moderately ill, 5=Markedly ill, 6=Severely ill, and 7=Extremely ill. Minimal improvement groups (rating of 3) for a fixed assessment contrast (e.g. Visit 3 vs. Visit 4, Visit 3 vs. Visit 5, and Visit 3 vs. Visit 6) define the MCIC anchor on Investigator-rated CGI-I and Caregiver-rated CGI-I. To define an MCIC anchor on CGI-S, the difference in severity ratings across assessment interval (e.g. Visit 4 minus Visit 3, Visit 5 minus Visit 3, and Visit 6 minus Visit 3) will be calculated with those exhibiting minimal improvement in severity across intervals used to define the MCIC anchor. Minimal improvement on CGI-S is calculated as a one category change of improvement, e.g. changing from a value of mildly ill at baseline to borderline ill at titration or markedly ill at baseline to moderately ill at maintenance.

To calculate MCIC for each of the CGI-I/CGI-S anchors defined above, PCH scores will be calculated by visit: Visit 4, Visit 5, and Visit 6. With three visits at which MCIC will be calculated, the three PCH variables may be expressed as $PCH_{3,4} = 100 * \left(\frac{V4-B}{B} \right)$, $PCH_{3,5} = 100 * \left(\frac{V5-B}{B} \right)$, and $PCH_{3,6} = 100 * \left(\frac{V6-B}{B} \right)$, where V4-B, V5-B, and V6-B are the difference in unweighted scores adjusted to 7 days between Visit 4 and baseline, Visit 5 and baseline, and Visit 6 and baseline, respectively. The MCIC values will be obtained from an ANOVA estimated using SAS' GLM procedure with PCH as outcome and the anchors: Investigator-rated CGI-I, Caregiver-rated CGI-I, and change in CGI-S scores as fixed independent classification variables. With three assessment occasions (Visit 4, Visit 5 and Visit 6) for which PCH will be calculated and three anchors (Investigator-rated CGI-I, Caregiver-rated CGI-I, and CGI-S) at each occasion there will be a total of 9 PCH and anchor combinations. A Separate one-way ANOVA will be fit for each of the 9 PCH and anchor combinations. Within a given PCH and anchor combination, the average PCH value for each level of the anchor will be estimated, with the MCIC estimate corresponding to the average PCH value for the minimal improvement group. Consistent with current best practice for MCIC reporting, (Hays et al., 2005) the ANOVA estimated 95% confidence interval for the MCIC estimates will also be provided. MCIC estimates will be triangulated in an attempt to establish the ability of the IA diary score to detect clinically meaningful change.

In addition, the cumulative distribution functions (CDFs) for PCH from baseline to each visit will be explored graphically. The CDFs for each anchor category stratum will be plotted for each assessment

combination (visit 3 vs. 4, visit 3 vs. 5, and visit 3 vs. 6), and within each assessment combination three anchor-specific CDF plots will be generated. Given that the CGI-I and CGI-S each have seven categories, CDFs for the CGI-I and CGI-S measures will display seven total CDFs. Given that the CGI-S has seven categories but the anchor will be converted to one-category change values for MCIC estimation, an additional CGI-S plot will be produced displaying six CDFs, one for each one-category change value (1 to 2, 2 to 3, . . . , 6 to 7) at each assessment combination in order to assess the uniformity of PCH across each possible one-point change combination. In addition, the CDFs for each treatment arm will be plotted. To augment the interpretation of the IA diary's ability to detect meaningful change, the MCIC estimates will be demarcated in the treatment-stratified CDF plots and the treatment-arm specific proportions achieving the MCIC estimates will be reported and compared.

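### Protocol 6.12: the nine raw mean PCH values for minimally improved children cannot, on their own, show that the diary detects change

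*Protocol*

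**What the plan says.** Protocol 6.12 evaluates whether PCH can detect change, using three anchors: investigator CGI-I, caregiver CGI-I and change in CGI-S. Each is taken at Visits 4, 5 and 6.

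- **Anchor groups.** For CGI-I: "Minimal improvement groups (rating of 3) for a fixed assessment contrast". For CGI-S: "Minimal improvement on CGI-S is calculated as a one category change of improvement".
- **Model.** "A Separate one-way ANOVA will be fit for each of the 9 PCH and anchor combinations". The mean PCH is estimated at every anchor level, "with the MCIC estimate corresponding to the average PCH value for the minimal improvement group".
- **Interval.** "the ANOVA estimated 95% confidence interval for the MCIC estimates will also be provided". This is an interval for the group mean, not for a difference between groups.
- **Conclusion.** "MCIC estimates will be triangulated in an attempt to establish the ability of the IA diary score to detect clinically meaningful change".
- **Graphs.** "The CDFs for each anchor category stratum will be plotted for each assessment" combination, as a graphical exploration. The MCIC values are also marked on the CDFs by treatment arm, and the proportions of each arm reaching them are reported and compared.

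The section names no contrast with the no-change group, no PCH-anchor correlation, no F or trend test and no acceptance criterion. SAP Section 1 leaves MCIC methods out of scope and assigns them to a designated CRO, so Protocol 6.12 is the only specification in the two documents.

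**The concern.** Responsiveness means that children whose anchor rating improves show a different PCH from children whose rating does not. The mean of one anchor level contains no such comparison. It also includes whatever change all children share, such as placebo response and possibly regression to the mean after entry on high severity.

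Triangulation does not repair this. Agreement among the nine values is what one would hope to see from a responsive diary, and also what one would see from a diary unrelated to every anchor. A threshold obtained in the second case would still be marked on the treatment CDFs and read as clinically meaningful. At stake is the interpretation of the diary score, not the efficacy test.

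**Working it through.** **1. The plan's own figures.** The documents state no MCIC value, expected mean PCH or anchor correlation, so there is nothing to reproduce except the count of combinations: 3 visits × 3 anchors = 9, which is correct.

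**2. The identity.** Let A be the anchor rating. If PCH is independent of A, then E[PCH | A = 3] = E[PCH], and E[PCH | A = 3] − E[PCH | A = 4] = 0. No distributional assumption is needed; skewness and the floor at −100 do not matter. The MCIC estimates the overall mean change at that visit, whichever anchor is used.

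**3. Size of the overall mean.** With the assumed drug effect in two of three arms, pooled mean = placebo mean − (2/3) × difference.

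- Protocol 6.10, difference 11.51: (2/3) × 11.51 = 7.7 points below placebo.
- SAP 3.5, difference 15: (2/3) × 15 = 10 points below placebo.

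The placebo mean is not given, so a range of 0 to −40 was used.

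**4. Precision.** Inputs: SD 27.3 (Protocol 6.10) or 34.83 (SAP 3.5, blinded review); N = 264 (Protocol 6.10, total as stated) or 3 × 122 = 366 (SAP 3.5). Both SDs refer to the primary endpoint over the whole treatment period; using them for by-visit PCH is an assumption. So are the anchor shares: 20% to 30% minimally improved in the simulation, and 30% minimally improved with 28% no change in the hand calculations. With N = 264 and SD 34.83:

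- Raw mean: n = 0.30 × 264 = 79.2; SE = 34.83/√79.2 = 3.91; 95% half-width about 7.7.
- Contrast: no-change n = 0.28 × 264 = 73.9; SE = 34.83 × √(1/79.2 + 1/73.9) = 5.63; half-width about 11.0.

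**5. Simulation with no association** (1,500 runs per setting, normal PCH, three equal arms, pooled ANOVA variance). Ranges cover shares of 20% and 30%. Exclusion of 0 is used here only as a yardstick.

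| N | SD | Difference | Placebo mean | MCIC (average) | CI of raw mean excludes 0 |
|---|---|---|---|---|---|
| 264 | 27.3 | 11.51 | 0 | −8 | 53–70% |
| 264 | 27.3 | 11.51 | −10 | −18 | at least 99% |
| 264 | 34.83 | 15 | 0 | −10 | 54–70% |
| 264 | 34.83 | 15 | −10 | −20 | 97–100% |
| 264 | 34.83 | 15 | −30 | −40 | 100% |
| 366 | 34.83 | 15 | 0 | −10 | 68–84% |
| 366 | 34.83 | 15 | −10 | −20 | 99.8–100% |

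In a separate setting with an overall mean of exactly 0, the MCIC averages about 0 and its CI excludes 0 in 4% of runs. Across all settings, the minimally improved minus no change contrast averages between −0.4 and +0.2, and its CI excludes 0 in 4% to 6% of runs, the nominal rate.

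**6. Triangulation.** With N = 264, SD 34.83, a 30% share and no association, all nine CIs exclude 0 in 12% of runs at a pooled mean of −10, 98% at −20 and 100% at −30. The nine values span about 10.5 points on average, so they agree only to within sampling error.

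**7. Proportions reaching the threshold.** If the threshold falls at the pooled mean (difference 15, SD 34.83, normal PCH), it lies 10 points below the placebo mean and 5 above the active mean. Placebo: Φ(−10/34.83) = 39%. Active: Φ(5/34.83) = 56%.

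**The case against.** The strongest reply is that Protocol 6.12 already provides most of what is needed. The same ANOVAs give the no-change mean, and the anchor-stratified CDFs would overlap if PCH were unrelated to the anchor. This stands: an attentive reader of the full output could see a lack of association. What remains is that no formal comparison or criterion is attached, and that only the MCIC estimates are named as the basis for the conclusion.

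The section follows a published recommendation for anchor-based group means, and Protocol 1.4 reports that the diary was found valid and reliable in a separate study. Complete independence is therefore an extreme case. It shows what the nine values can and cannot demonstrate; it is not a forecast. The CRO may also hold a fuller specification that is not visible here.

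Three stronger readings are tempting but unsupported:

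- **That the plan treats a CI excluding 0 as proof of responsiveness.** Protocol 6.12 only says that the interval will be provided.
- **That the rule always returns a clearly non-zero MCIC.** It does so only if the overall mean PCH is away from 0. With the assumed drug effect alone and no placebo change, the CI excludes 0 in about 53% to 84% of runs.
- **That about half of every arm would reach an uninformative threshold.** Under the SAP's figures it is about 39% and 56%, so the arm comparison still reflects the treatment difference. Only the label of clinical importance is in doubt.

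**Conclusion.** The point holds in limited form. Nine raw means for the minimal-improvement groups cannot by themselves establish that PCH detects clinically meaningful change, because without any association they reproduce the overall mean change and still agree. This follows from the definition of the estimator; only the illustrative sizes rest on the assumed placebo means, anchor shares and SD.

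A reader might infer that the whole section is unable to tell a responsive diary from an unresponsive one. The documents do not support that, since the level means and CDFs are planned. The gap is that they carry no criterion and sit outside the stated conclusion. MCIC is a supportive, end-of-study analysis outside the primary and secondary objectives, and the primary and secondary tests, Type I error and sample size are not touched. This is a cheap improvement.

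**What to change.** In Protocol 6.12, before unblinding:

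- Base the responsiveness conclusion on the minimally improved minus no change contrast with its 95% CI, from the same nine ANOVAs. For CGI-S, use one-category improvement minus no category change.
- Add the Spearman correlation of PCH with each anchor at each visit.
- Keep the raw mean of the minimal-improvement group as the MCIC, labelled as within-group change.
- Show the contrast and correlation beside any threshold marked on the treatment CDF plots.

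Do not make statistical significance of the contrast a condition for showing a threshold. With SD 34.83 and the assumed shares, a true 10-point step would be detected with power Φ(10/5.63 − 1.96) = 43% at N = 264. At N = 366, SE = 34.83 × √(1/109.8 + 1/102.5) = 4.78, giving Φ(10/4.78 − 1.96) = 55%. Such a condition would often discard a sound anchor.

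The cost is one contrast statement per ANOVA and nine correlations, with no new data. The downside is a wider interval: a half-width of about 11.0 points against 7.7 for the raw mean at N = 264.

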6.13 Pharmacokinetic Analyses

6.14 Safety Analyses

Evaluation of safety will be performed for the safety population. Safety data that will be evaluated include concomitant medications, AEs, clinical laboratory results, vital signs, ECGs, and findings from the physical examinations. The occurrence of neurological side effects will be assessed by looking at any worsening in scores from Visit 3 to each subsequent visit for each of the Simpson-Angus scale, Barnes Akathisia scale, and AIMS. Suicidal ideation and suicidal behavior will be measured by C-SSRS.

All summary tables related to safety analyses will use the safety population.

6.14.1 Adverse Events

AEs will be classified into standardized medical terminology from the verbatim description (Investigator term) using the Medical Dictionary for Regulatory Activities (MedDRA). AEs will be summarized using discrete summaries at the subject and event level by system organ class and preferred term for each treatment group. Similarly, treatment-emergent AEs will be summarized by severity and relationship separately. Verbatim description and all MedDRA level terms, including the lower level terms, for all AEs will be contained in the subject data listings.

All AEs occurring after randomization and throughout the study period will be recorded. For subjects who receive SM, treatment-emergent AEs (TEAEs) will be collected starting after the first dose of SM (Visit 3) to the end of the study. These AEs include those that emerge during treatment or worsen in severity during treatment. These AEs will be tabulated, listed and analyzed.

Separate TEAE incidence tables will be presented for the three treatment groups. The incidence rates for all SADRs will also be summarized as described for all TEAEs.

In addition, these same tables will be presented by treatment period (Titration, Maintenance, and combined Titration and Maintenance). For the combined Titration and Maintenance Periods, the incidence of TEAEs will also be presented by highest severity reported and the dose of SM at first occurrence.

Listings (and tabular summaries, if warranted) of deaths, other SAEs, and other significant TEAEs, including TEAEs resulting in treatment discontinuation, will be provided.

6.14.2 Laboratory Values

Clinical laboratory values will be summarized by visit by treatment group using descriptive statistics for hematology and biochemistry. For quantitative laboratory parameters, both actual values and change from baseline values will be summarized.

Laboratory test results will be assigned a low, normal, high (LNH) classification according to whether the values were below (L), within (N), or above (H) the laboratory parameters' reference ranges provided by the central laboratory. Within-treatment comparisons will be based on three by three tables (shift tables) that, for a particular laboratory test, compare the LNH classification at baseline to the LNH classification at visit. By subject-listings of all abnormal laboratory values, i.e., those with L or H classification will be provided.

6.14.3 Vital Signs, Height and Weight

Vital signs will be summarized by visit by treatment group using descriptive statistics. Both actual values changes from baseline to visit will be summarized. Descriptive summary statistics (mean, SD, median, and range) for vital sign data, height, weight and BMI will be evaluated by treatment group.

6.14.4 ECG Results

By-visit tabular summaries of the quantitative ECG parameters and the overall ECG findings (normal, abnormal not clinically significant, or abnormal clinically significant) will be presented. The QT will be corrected using Fridericia's method.

ECG results will be summarized by visit by treatment group using descriptive statistics (for quantitative ECG parameters) and frequency tables (for qualitative ECG parameters, including the overall ECG finding). For quantitative ECG parameters, both actual values and change from screening values will be summarized.

6.14.5 Physical Examinations

Findings from the physical examinations will be listed for each system or area examined.

6.14.6 Columbia Suicide Severity Rating Scale (C-SSRS)

C-SSRS outcomes will be summarized using number and percent of subjects by categories for suicidal ideation only, suicidal behavior only and suicidality (ideation and behavior combined). The summary will be presented by treatment groups. The proportion of subjects in each treatment group will be compared with the proportion of subjects in the placebo group using Fisher's exact test or Chi-square test as applicable if appropriate.

6.14.7 Infrequent Behaviors Checklist

Infrequent behaviors will be listed for each subject by treatment group.

6.14.8 Other Special Tests

The occurrence of neurological side effects will be assessed by looking at the changes in scores from baseline to post-baseline visits for each of the Simpson-Angus scale, Barnes Akathisia scale, and AIMS. For each item on each of these scales, the number (and percentage) of subjects with a worse score at any post-baseline visit, compared to baseline, will be presented. A listing of these subjects will also be provided.

7 DOCUMENTATION

7.1 Adherence to the Protocol

The Investigator agrees, when signing the protocol, to adhere to the instructions and procedures described in the protocol and to adhere to the principles of ICH GCP to which the protocol conforms as well as all governing local regulations and principles for medical research.

The protocol, ICF, and appropriate related documents must be reviewed and approved by an IRB constituted and functioning in accordance with ICH E6 and any local regulations. Documentation of IRB compliance with the ICH and any local regulations regarding constitution and review conduct will be provided to the Sponsor.

A signed letter of study approval from the IRB Chairman must be sent to the Investigator with a copy to the Sponsor prior to study start and the release of any SM to the site by the Sponsor or its designee. If the IRB decides to suspend or terminate the study, the Investigator will immediately send the notice of study suspension or termination by the IRB to the Sponsor.

Study progress is to be reported to IRB annually (or as required) by the Investigator or Sponsor, depending on local regulatory obligations. If the Investigator is required to report to the IRB, he/she will forward a copy to the Sponsor at the time of each periodic report.

7.2 Changes to the Protocol

There are to be no changes to the protocol without written approval from the Sponsor.

Any change to the protocol requires a written protocol amendment or administrative change that must be approved by the Sponsor before implementation. Amendments specifically affecting the safety of subjects, the scope of the investigation, or the scientific quality of the study require additional approval by the applicable IRBs and, in some countries, by the regulatory authority. These requirements should in no way prevent any immediate action from being taken by the Investigator, or by the Sponsor, in the interest of preserving the safety of all subjects included in the study. If an immediate change to the protocol is warranted as per the Investigator, for safety reasons, the Medical Monitor and IRB must be notified promptly.

Changes affecting only administrative aspects of the study do not require formal protocol amendments or IRB approval, but the IRB must be kept informed of such changes. In these cases, the Sponsor will send a letter to the IRB detailing such changes.

7.3 Protocol Deviations

There are to be no Investigator-initiated deviations from the protocol. Any subject whose treatment deviates from the protocol or who is not qualified for study participation may be ineligible for analysis and may compromise the study. The date of and reason for deviations must be documented in all cases. Significant or major protocol deviations impacting the safety of the subject or the integrity of the study must be reported by the Investigator to the IRB immediately. Reporting of all other protocol deviations must adhere to the requirements of the governing IRB. Protocol assessments will continue until the end of the study, unless the protocol deviations put the subject at risk or the subject's condition requires that he/she be discontinued from the study.

7.4 Data Quality Assurance

This study will be organized, performed, and reported in compliance with the protocol, standard operating procedures (SOPs), working practice documents, and applicable regulations and guidelines. Site visit audits may be made periodically by the Sponsor's Quality Assurance team or qualified designee, which is an independent function from the study conduct team.

7.4.1 Data Collection

The primary source document will be the subject's medical record. If separate research records are maintained by the Investigator(s), both the medical record and the research record will be considered the source documents for the purposes of monitoring and auditing the study.

Electronic data collection techniques will be used to collect data directly from the study sites using eCRFs. The electronic data will be stored centrally in a fully validated clinical database.

[REDACTED]
[REDACTED]
[REDACTED]
[REDACTED] /programs.

Data recorded on source documents will be transcribed into the eCRFs in accordance with the eCRF Completion Instructions that are provided to the study sites. The Investigator is responsible for ensuring that all sections of each eCRF are completed correctly, and that entries can be verified against source documents. The eCRFs will be monitored for completeness and accuracy against the source documents by the CRA(s) on a regular basis. Inconsistencies between the eCRFs and source documents will be resolved in accordance with the principles of GCP.

Completed eCRFs will be extracted from the clinical database, stored as PDF files on a CD-ROM and sent to the respective study site for archiving. A CD-ROM containing all eCRFs will be kept by the Sponsor in the Sponsor's Trial Master File.

